For patients with qualifying bleeding (rated on initial evaluation as at least “mild”) who have been randomized to receive Surgicel Snow, a single thin layer of dry Surgicel Snow will be applied over the area of bleeding and positioned firmly in direct contact to the areas of bleeding with blunt surgical instruments. Surgicel Snow will be left in the cavity to be absorbed. Dry gauze will not be placed over the material. No adjuncts will be added to enhance hemostasis, but patients with small arteriolar bleeding will have pressure maintained on the bleeding site for 60 seconds. Control patients will be managed with direct compression with gauze pads or laparotomy pads for four minutes. If hemostasis is not achieved by compression after four minutes, the source and rate of bleeding will be reevaluated and management will be determined by the surgeon. If the surgeon uses Surgicel Snow to achieve hemostasis at some point after 4 minutes, the patient will be included in the control group, but his/her data will be and flagged for the analysis.

Hemostasis will be defined as the absence of free-flow bleeding, specified as no new appearance of blood from the bleeding site. Pinpoint or petechial bleeding that appears but does not grow, or saturation of blood into the hemostat that may have occurred prior to or during the application of hemostatic agent that did not spread during the observation period, will not be considered free-flow bleeding. Control and treatment patients who do

[figure not shown]
not require a topical agent to achieve hemostasis, thus not requiring a bleeding evaluation will be excluded from the study.

For control patients, hemostasis failures at 4 minutes will be managed as per judgment of the primary surgeon, most likely be the use of a topical sealant. For treatment patients, hemostatic failure at 4 minutes will be reassessed for rate of blood loss and if the rate of loss is estimated at less than 25 cc per minute, additional observations will be made at 7 and 10 minutes. If failure of hemostasis at 4 minutes with an estimated loss of ≥ 25 cc/min, patient will be managed as per judgment of surgeon. Persistent bleeding at the 10 minute observation point will be treated as per the surgeon's judgment. The nature of the bleeding will be recorded throughout the study.

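### After 4 minutes the two arms are observed on different schedules, and the endpoint text gives no failure minute, censoring rule or time value for patients managed further

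*Combined protocol and SAP*

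**What the plan says.** **Control arm (Design).** "Control patients will be managed with direct compression with gauze pads or laparotomy pads for four minutes". Then: "If hemostasis is not achieved by compression after four minutes, the source and rate of bleeding will be reevaluated". The section later adds "For control patients, hemostasis failures at 4 minutes will be managed as per judgment of the primary surgeon", and expects this to "most likely be the use of a topical sealant". No further look is scheduled. A control given Surgicel Snow after 4 minutes stays in the control group and is flagged, but no time or outcome value is assigned.

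**Surgicel arm (Design).** A patient still bleeding at 4 minutes has the bleeding rate assessed once more. The next step is conditional: "if the rate of loss is estimated at less than 25 cc per minute, additional observations will be made at 7 and 10 minutes". Above that rate: "If failure of hemostasis at 4 minutes with an estimated loss of ≥ 25 cc/min, patient will be managed as per judgment of surgeon". At the end of the extra looks: "Persistent bleeding at the 10 minute observation point will be treated as per the surgeon's judgment".

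**Endpoints (Assessment of Efficacy).** Time to hemostasis is primary. Failure to reach hemostasis is also named as a clinical endpoint, with no minute attached.

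**Analysis (Statistical Analysis).** The arms will be compared on the primary and secondary outcomes, with multivariate adjustment, at p < 0.05. No test, censoring rule or rule for rescued patients is given.

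**Not available.** The Intraoperative Flow Diagram is not shown. Direct Access to Source Data Documents says that a data collection sheet sets out when data points are collected, but the sheet is not among the documents.

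**The concern.** After 4 minutes only the Surgicel arm has scheduled chances to record hemostasis on its assigned treatment. A control still bleeding at 4 minutes either has no hemostasis time or has one produced by another treatment, and the text does not say which to enter. Two analysts could follow the available text and score the same patients differently. Some scorings create a difference between arms whose bleeding stops at identical times, and the direction of that difference depends on the unstated rule. Because the trial is not blinded, the rule should be on paper before the arms are compared.

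**Working it through.** **The plan's own figures.** The Design section gives 60 patients, 30 per arm, in blocks of 10: 60/10 = 6 blocks, and 60/2 = 30 per arm. No power, effect size or hemostasis rate is stated, so there is no planned figure to reproduce on this point.

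**Assumptions not in the documents.** Stopping times are exponential and identical in both arms. Hemostasis by 4 minutes is p4 = 50/60/70/80/90%. There are 30 evaluable patients per arm, and tests are two-sided at 0.05. The tests are my choice, since the plan names none. L is the share of Surgicel 4-minute failures that go straight to the surgeon's judgment.

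**Why L is unknown.** The bleeding-rate footnote in Background uses cc per 10 seconds. Multiplying by 6 gives mild 12–18 and moderate 18–30 cc/min. The 25 cc/min threshold (25/6 = 4.2 cc per 10 s) lies above the mild band but inside the moderate one. I therefore vary L.

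**Formulas.** With f4 = 1 − p4, the hazard is −ln(f4)/4. A patient bleeding at 4 minutes is still bleeding at 10 with probability f4^1.5. Surgicel failure at the last look is f4 × [L + (1 − L) × f4^1.5].

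**1. Primary endpoint, rank test, failures ranked worst, first look at 4 minutes in both arms.** Take p4 = 50% and L = 0.
- Controls: 50% have time 4 and 50% are worst.
- Surgicel: 50% have time 4. Still bleeding at 10 is 0.5^2.5 = 17.7%, so 50 − 17.7 = 32.3% are recorded at 7 or 10.
- Pairs in which one patient stopped by 4 minutes and the other did not cancel between arms. What remains is 0.323 × 0.50 = 0.16 net in favor of Surgicel, with no true effect.

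Simulated rejection (10,000 trials per setting):

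| p4 | 50% | 60% | 70% | 80% | 90% |
|---|---|---|---|---|---|
| L = 0 | about 22% | 15% | 9% | 5% | 5% |
| L = 0.5 | about 9% | 7% | 6% | 5% | 5% |

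Repeat runs differ by one or two points.

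**2. Same test, L = 0, but 90% of rescued controls receive a hemostasis time 0.5–3 minutes after the 4-minute look (assumed).** At p4 = 50%, controls become 50% at time 4, 45% between 4.5 and 7, and 5% worst. The net is 0.323 × 0.05 − 0.323 × 0.45 − 0.177 × 0.45 = 0.016 − 0.145 − 0.080 = −0.21, now in favor of control. Rejection is about 32/18/9/5/5% across the five rates, with the excess toward control at the lower ones.

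**3. Failure endpoint, Fisher's exact test, exact enumeration.**

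| Failure read at | 50% | 60% | 70% | 80% | 90% |
|---|---|---|---|---|---|
| Each arm's last look, L = 0 | 68% | 70% | 64% | 42% | 7% |
| Each arm's last look, L = 0.5 | 17% | 16% | 13% | 8% | 2% |
| 4 minutes in both arms | 2.7% | 2.6% | 2.6% | 2.2% | 0.9% |

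In the first row the failure rates compared (control vs Surgicel) are 50 vs 18, 40 vs 10, 30 vs 5, 20 vs 2 and 10 vs 0.3%, which come from the schedule alone.

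**The case against.** The best defense is that the Design section already uses one definition: it speaks of failure at 4 minutes in both arms and calls bleeding at 10 minutes persistent, not failed. On that reading the failure endpoint is sound, at 0.9–2.7%. Crossovers are also kept in their assigned arm and flagged. The look times may be in the flow diagram, the data collection sheet or the cited study whose methods the primary endpoint modifies.

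Much of this stands. A reader might infer that the trial carries a false-positive risk near 70%. The documents do not support that: the figure concerns the failure endpoint, not the primary one. It needs failure to be read at each arm's last look, against the 4-minute wording in Design, with no treated failure leaving at 4 minutes. A reader might also infer a bias from Surgicel sites being visible earlier, because gauze is not laid over them while controls are under pads. No look before 4 minutes is scheduled in either arm, so that is conjecture. Nor should one conclude that no rule exists anywhere, or that control failures are dropped.

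What remains is that Design uses failure at 4 minutes to direct management, and the endpoint text does not adopt it. The flag gives crossovers no time. Even a sheet that lists look times would not by itself settle censoring or the scoring of rescued patients. The Design statement that the nature of bleeding is recorded throughout is not a schedule.

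**Conclusion.** The point holds for the available text. Scheduled observation is unequal after 4 minutes, and the endpoint and analysis sections do not say how to score patients managed beyond that time. For the primary endpoint the illustrated false-positive rate reaches about 22% toward Surgicel, or about 32% mainly toward control, depending on the unstated rule. It is near 5% when 4-minute hemostasis is 80% or more, and falls when more treated failures leave at 4 minutes. All sizes rest on assumed exponential times, hemostasis rates and tests, and on 30 evaluable patients per arm. The documents give no hemostasis rate, so the actual bias is unknown. This is a should-fix: a common 4-minute assessment already exists, and the repair is wording.

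**What to change.** Change the endpoint and analysis wording only; patient management stays as written.

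1. In Assessment of Efficacy, define failure as no hemostasis at 4 minutes in both arms, and state time zero in each arm.
2. Count anyone managed further after a 4-minute failure, including controls given Surgicel Snow, as a 4-minute failure in the assigned arm with no later hemostasis time.
3. Limit the formal comparison of hemostasis to the first 4 minutes, censoring time to hemostasis at 4 minutes in both arms. If the first look is at 4 minutes, this is a yes/no comparison. Report it as such, with a risk difference and 95% CI; a log-rank label would add nothing. If earlier times are recorded the same way in both arms, they can be used.
4. Report the 7- and 10-minute Surgicel looks descriptively.

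If the flow diagram or data collection sheet already sets these rules, copy them into Assessment of Efficacy.

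**Cost.** No new data are needed, because Design already assesses both arms at 4 minutes. The price is that there is no formal comparison after 4 minutes, and precision is limited. With 30 per arm, the Newcombe 95% CI is about ±17 points when both arms are at 90% and about ±24 points when both are at 50%. Record the change before outcomes are compared.

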
Design:

The proposed research method will use a randomized, concurrent control, no blinding. We are limiting our study to retroperitoneal dissection hysterectomy only to control for the expected variation in bleeding among the potential procedures. We propose to randomize 60 patients - 30 to the treatment group and 30 to the control group. The patients participating in this study would be patients scheduled for hysterectomy at Norwalk Hospital and Danbury Hospital under the direction of [name], [name], and [name].

The patient population is drawn from throughout the State of Connecticut. Indications for hysterectomy will include benign, complex benign uterine and adnexal pathology, as well as gynecologic oncology cases. Vaginal hysterectomy procedures and open abdominal procedures will be excluded. Complex benign pathologies are those that are likely to require retroperitoneal dissection and or ureterolysis, (e.g., cervical leiomyoma, endometriosis, etc.

Peritoneal access for hysterectomy will include open laparotomy, standard multiport laparoscopy, and robotic assisted laparoscopy. All patients scheduled for indicated procedures will be screened for inclusion. Once consented, patients will be randomized to the control group or the treatment group. The control group will receive standard of care, and the treatment group will receive Surgicel Snow. A random number generator will be used to determine test vs. control in blocks of 10.

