Because multiple factors other than retroperitoneal bleeding contribute to the total intraoperative blood loss, we believe that the intraoperative estimated blood loss is not a pure indicator of the efficacy of a topical hemostatic agent for control of retroperitoneal bleeding. The determination of the primary endpoint of time to hemostasis is based upon a modification of the methods used by Hutchinson, et al in Cellulose (15). Secondary endpoints will include total operative time, intraoperative blood loss, blood transfusion, postoperative hemoglobin decrease, rate of postoperative symptomatic fluid collection,

postoperative pelvic abscess, and total cost for care from day of operation until six week (+/- 1 week) postoperative visit.

Assessment of Safety:

Whereas Surgicel Snow is generally used for minimal to mild bleeding from focal or widespread sources, should there be an adverse event related to the study conduction, this will be documented and reported to the study's PI. The PI will evaluate whether the adverse event involves risk to participants or others. If so, the PI may choose to change the protocol, change the consent form, require that all participants already enrolled be notified and/or re-consented, or suspend or terminate the study.

Statistical Analysis:

All data will be collected in paper format and transferred to an electronic database where all PHI will be removed and replaced with a study number. After conducting descriptive analyses, we will compare the treatment and control group on the primary and secondary outcomes. Multivariate analyses will be used to control for any observed variation between the study groups. Statistical significance will be assessed at $p < 0.05$.

It is anticipated that 60 participants will be enrolled in this study. The study will be terminated once all patients have completed their 6 week (+/- 1 week) follow-up post-surgery.

Direct Access to Source Data Documents:

The study's data collection sheet outlines when each data point will be collected. The study's PI, primary study coordinator, and co-authors will have access to all study data. These data will be used for study purposes only, and will be stored on a password-

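### Preoperative hemoglobin should always be in the model for postoperative hemoglobin decrease, and the plan should say how a transfused patient's value counts

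*Combined protocol and SAP*

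**What the plan says.** The Assessment of Efficacy section makes time to hemostasis the primary endpoint. Hemoglobin is one of seven items in the secondary list, which includes "blood transfusion, postoperative hemoglobin decrease, rate of postoperative symptomatic fluid collection". Transfusion is thus a separate endpoint beside the hemoglobin fall that it can alter.

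The Statistical Analysis section gives one analysis for all outcomes. After descriptive summaries, "we will compare the treatment and control group on the primary and secondary outcomes". On covariates it says: "Multivariate analyses will be used to control for any observed variation between the study groups". Significance is judged at p < 0.05.

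The section names no test, model or covariate for hemoglobin. The available text does not give the time of the postoperative sample or say whether it comes before or after a transfusion. The Design section sets 30 patients per arm without blinding.

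**The concern.** There are two separate gaps.

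**Baseline adjustment.** A decrease cannot be computed without the preoperative value, so that value will be on file for every patient analyzed. Under the stated rule it is used as a covariate only if the arms happen to differ on it. A baseline covariate earns its place by predicting the outcome, not by being unbalanced. Tying its use to an observed difference may give up precision in a small trial. It also leaves the model to be chosen after the data are seen.

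**Transfusion.** A transfusion raises measured hemoglobin. If the sample is drawn afterwards, a patient who bled heavily and was transfused shows a smaller fall than she had. If more patients are transfused in one arm, that arm's mean fall is understated. The trial is open-label, so decisions to transfuse could also differ by arm for reasons other than blood loss.

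**Working it through.** **The plan's own figure.** The only figure to reproduce is the sample size: "We propose to randomize 60 patients - 30 to the treatment group and 30 to the control group". It cannot be reproduced, because no power, effect size, SD or event rate is given for any endpoint. All hemoglobin inputs below are therefore assumptions.

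**Precision.** Let the preoperative SD be 1, the postoperative SD be k, and their correlation be r.

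- Change-score variance: 1 + k² − 2rk.
- ANCOVA variance: k²(1 − r²).
- Change score minus ANCOVA: (1 − rk)², where rk is the slope of post on pre.

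ANCOVA is therefore never less precise, apart from one residual degree of freedom (57 instead of 58 with 60 patients). The gain is zero when the slope is 1. With equal SDs (k = 1) the variances are 2(1 − r) and 1 − r², and their ratio is (1 + r)/2. The last two columns give the difference detectable with 30 per arm, 80% power and two-sided 5% (sidedness is not stated in the plan). They use (1.960 + 0.842) × √(2/30 × variance), in SDs of a single hemoglobin value.

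| r | Change variance | ANCOVA variance | Ratio | Detectable, change | Detectable, ANCOVA |
|---|---|---|---|---|---|
| 0.5 | 1.00 | 0.75 | 0.75 | 0.723 | 0.626 |
| 0.7 | 0.60 | 0.51 | 0.85 | 0.560 | 0.517 |
| 0.8 | 0.40 | 0.36 | 0.90 | 0.457 | 0.434 |
| 0.9 | 0.20 | 0.19 | 0.95 | 0.323 | 0.315 |

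A ratio of 0.75 equals 1/0.75 = 1.33 times the patients, and 0.90 equals 1/0.90 = 1.11 times.

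A case with no gain is r = 0.8 and k = 1.25, where the slope is 0.8 × 1.25 = 1. Change variance is 1 + 1.5625 − 2(0.8)(1.25) = 0.5625. ANCOVA variance is 1.5625 × (1 − 0.64) = 0.5625.

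**Masking by transfusion.** If every transfused patient is sampled afterwards, the bias in the between-arm difference is (difference in proportions transfused) × (rise per transfused patient).

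- 3/30 v 0/30, rise 1 to 2 g/dL: 0.10 × 1 = 0.10, up to 0.10 × 2 = 0.20 g/dL.
- Low end, 1/30 v 0/30 with a rise of 1: 0.03 g/dL.
- High end, 6/30 v 2/30 with a rise of 2: 0.133 × 2 = 0.27 g/dL.
- Equal proportions, such as 3/30 in each arm: 0.

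**Illustrative simulation.** There were 200,000 patients per arm, with preoperative mean 12.5 and SD 1.3 g/dL, and a mean fall of about 1.5 with SD 1.0. Patients below a hemoglobin cut-off of 7 or 8 g/dL gained 2 g/dL. The cut-off serves only to generate data and is not a clinical rule.

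| Cut-off | True difference | Observed difference | Transfused, by arm |
|---|---|---|---|
| 7 | 0.496 | 0.478 | 1.6% v 0.7% |
| 7 | 0.996 | 0.944 | 3.4% v 0.8% |
| 8 | 0.501 | 0.442 | 6.4% v 3.4% |
| 8 | 1.001 | 0.843 | 11.3% v 3.4% |

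The loss runs from (0.496 − 0.478)/0.496 = 4% to (1.001 − 0.843)/1.001 = 16%. With no true difference there was no bias, and the arms were never reversed. The same cut-off applied in both arms, so the simulation does not cover transfusion decisions that differ by arm. For those the masking formula applies, and it can give a bias even with no true effect.

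**The case against.** The strongest reply is that the plan names no model for any endpoint, so this is missing detail and not a wrong analysis. A reader might infer that hemoglobin will be analyzed as an unadjusted raw change. The documents do not say so, and the multivariate sentence could admit the preoperative value. That much of the reply stands. It does not remove the point, because the one adjustment rule the plan does state depends on observed imbalance.

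Timing may also be settled elsewhere. The section on access to source data refers to a data collection sheet that sets when items are collected, and that sheet is not in the available text. It may fix the sampling time, but a sampling time would supply neither a rule for transfused patients nor a model.

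A reader might further infer that transfusion will make the worse arm look better. The documents do not support this. It needs both a post-transfusion sample and unequal transfusion between arms, and the simulation showed attenuation without reversal. The Objectives limit the study to minimal or mild bleeding, or moderate bleeding already reduced, so transfusion may be uncommon; no rate is given. Transfusion is reported separately, so an imbalance would be visible, though seeing it does not correct the hemoglobin result.

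Finally, it is not true that a change score loses precision whenever the correlation is below 1. The case with slope 1 shows no loss.

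**Conclusion.** The point holds as a minor one. Always adjusting for a value that the endpoint already requires improves on adjusting only after an imbalance is seen, at the price of one degree of freedom. Under equal SDs the variance ratio is 0.75 at r = 0.5 and 0.90 at r = 0.8. It approaches 1 as the slope of post on pre approaches 1, and the documents give no figure for r or for the SDs.

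The absence of a transfusion rule is a real gap in the available text, with a modest and conditional effect: 0.10 to 0.20 g/dL in the 3/30 v 0/30 case, and 0.03 to 0.27 g/dL over the unequal cases tried. For scale, if the fall has an SD of 1.0 g/dL, as the simulation assumed, 30 per arm detects about 0.72 g/dL at 80% power. One secondary endpoint is affected, and the primary endpoint is not.

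**What to change.** 1. State that postoperative hemoglobin will be analyzed by ANCOVA with treatment arm and preoperative hemoglobin in the model, whatever the observed balance. The treatment estimate is the same, apart from sign, whether the outcome is the postoperative value or the decrease, so the endpoint itself does not change.
2. State the time of the postoperative sample, or cite the data collection sheet if it is fixed there.
3. Prespecify a rank-based sensitivity analysis for transfusion. For a transfused patient, use a value taken after surgery began and before the first transfusion where one exists; otherwise rank her as worst. Never use the preoperative value for this purpose. For a patient transfused during surgery it would score her decrease as zero, and the worst-rank rule would never apply. ANCOVA alone does not correct for transfusion, so this step is needed as well.

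The cost is a few sentences of analysis text, one data-sheet field for the time of each hemoglobin sample relative to transfusion, and one degree of freedom. No extra blood draw and no change to patient care is needed.
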